The primary objective of this protocol is to investigate whether ghrelin alters alcohol's pharmacologic effects, including motivation for alcohol reward, as well as subjective measures of craving, and the subjective responses to alcohol in heavy drinkers receiving IV administrations of ghrelin and alcohol.

a. Primary objectives

The primary measure of this study will be the breakpoint, which is the schedule (number of button presses) at which the individual stops to work for more alcohol.

b. Secondary objectives

Secondarily, the BrAC exposure measures will also be determined, that is the highest (max) BrAC, average BrAC and the area under the BrAC-time curve determined for each subject. Urge to drink and alcohol sensitivity will be measured during the PR session. Adverse events will also be assessed in order to assess the safety of the IV co-administration of ghrelin and alcohol. Also, during the "fMRI/alcohol clamp" session, fMRI will be used to see whether ghrelin affects the activation of the ventral striatum (VS) in anticipation to work for alcohol reward and the incentive salience of cues in subjects who will subsequently receive IV alcohol administration. In

addition to the VS, other fMRI ROI's are the amygdala, insula and OFC. Adverse events will also be assessed during the fMRI/alcohol clamp sessions.

Furthermore, an additional secondary aim will be an exploratory analysis of the role of genetic polymorphisms of both ghrelin and ghrelin receptor genes – detailed in page 14 – as possible moderators of ghrelin's effects on the primary aim ('breakpoint', i.e. number of button presses in the IV alcohol PR procedure).

3. Subjects:

a. Description of study populations

Male and female adults will be eligible to participate in this study. Participants will be non-treatment seeking heavy drinking volunteers. Our goal is to screen 124 subjects and recruit 62 individuals. Assuming a 20% drop-out rate, we will reach 50 completers.

b. Inclusion criteria

1. Male and female participants between 21-60 years of age.
2. Good health as determined by medical history, physical exam, ECG and lab tests.
3. Creatinine \leq 2 mg/dl.

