The present protocol will be submitted for review to the FDA. [name] holds an IND for the use of IV ghrelin in alcohol-dependent heavy drinkers for the trial performed at Brown University. The FDA submission for this protocol will cross-reference the previous IND (notably, we will use ghrelin from the same lot#). Furthermore, [name] holds an IND for the use of IV ethanol, which will be cross-referenced as well.

There is a possibility that subjects might identify if they received IV ghrelin or placebo. Therefore, at the end of each session, we will ask subjects if they believe they received ghrelin or placebo and this information will be recorded.

7. Risks and discomforts

IV Ghrelin administration

There is a potential risk of side-effects from infusion of ghrelin, although side-effects have not been frequent, and when side-effects were reported, they were all in the mild range (see Tables 1 and 2 above). No clinically significant, serious or unexpected side-effects have ever been reported in the published literature to date. It should also be noted that the previous study conducted at Brown by [name] shows a very safe profile of IV ghrelin when administered to non-treatment seeking heavy drinking alcohol-dependent volunteers.

Risks will be minimized through careful and detailed screening of participants to minimize recruitment of those who might be at higher risk for adverse events, as well as careful and detailed monitoring of adverse events and participant well-being during the laboratory sessions.

1. Consistent with the well-known effect of ghrelin on food intake, hunger and craving for food may occur after IV ghrelin administration.
2. IV Ghrelin has been associated with flushing, facial warmth and sweating. This side-effect, however, was never reported in the IV ghrelin study with alcoholic individuals at Brown University, and in that study history of flushing (e.g. alcohol-induced flushing reactions) was not an exclusion criterion. Nonetheless, in this study involving the IV administrations of ghrelin and alcohol, potential individuals with current or prior history of alcohol-induced flushing reactions will be excluded.
3. IV Ghrelin has been associated with decreased arterial pressure and secondary increased heart rate can also occur. In this study, we will exclude individuals with history of hypotension clinically significant (e.g.: history of fainting and/or syncopal attacks) as well as those with resting systolic BP < 100mg.

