Administration of alcohol to pregnant women might cause harm to the fetus. No fetus will be exposed to ethanol. A urine pregnancy test will be administered during each study visit block to all women. A positive test for beta-hCG would exclude participation in the study. Should a positive test occur, the investigators will be informed, and the PI or Medical Investigator will be involved in gently informing the participant of the fact, and will offer referral to an obstetrician.

IV Ghrelin and IV alcohol co-administration

There is a potential risk for additive effects of ghrelin and alcohol co-administered, such as:

- Flushing and facial warmth; thus, we will exclude individuals with current or prior history of alcohol-induced flushing reactions.
- Sedation; thus, we will exclude subjects who take medications that may amplify alcohol's sedative effects and we will only enroll individuals who are not older than 60.
- Decreased arterial pressure; thus, we will exclude individuals with history of hypotension clinically significant, and blood pressure and continuous heart rate will be monitored during the lab and fMRI sessions. Furthermore, subjects whose screening will show resting systolic BP < 100 mmHg are not enrolled in this study.

As shown in Tables 1 and 2 above, the IV administration of ghrelin has a very safe profile, and we anticipate that its administration together with alcohol administration will be safe and well-tolerated. Also, subjects will be continuously monitored during the lab sessions and alcohol and ghrelin administrations will be stopped (and the IRB notified) if a subject should develop any significant symptoms requiring to do so. Not only the sessions are performed in a well-controlled environment in the NIH Clinical Center, but subjects will be kept overnight at the hospital and only released the morning after in order to maximize their safety and monitoring.

Risk of fMRI

1. *Anxiety about enclosed spaces*- Some individuals experience claustrophobia when placed inside the magnet bore of the scanner. Participants will be warned about this in advance and advised not to participate if they are prone to experiencing anxiety in enclosed places.

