2. *Nerve stimulation*- The use of a 3T field strength magnet sometimes induces "peripheral nerve stimulation," in which peripheral muscles twitch in association with scanning. Subjects will be notified of this possibility in the consent form. The twitching does not occur in everyone, is not painful, and usually lasts for a short time. Some individuals may find this mildly annoying and we will terminate the scanning if they feel uncomfortable. Finally,

fMRI is a noisy process, so we require participants to wear foam earplugs while inside the scanner.

Insertion of IV lines

The total amount of blood to be drawn for this protocol will be approximately 428cc (= 87 US teaspoons). There is a slight risk of bruising or, rarely, infection from insertion of indwelling peripheral venous catheters for infusion and blood sampling. Risks from IV catheterization are minimized by experienced medical personnel who will perform catheter placement using sterile technique and following universal precautions. Participants will be seated or supine when catheters are placed.

8. Subject Safety monitoring

Subjects will be monitored regularly and frequently during their participation in the study. They will undergo standard assessment battery (described below) at each study visit.

Parameters to be monitored (see Study flow sheet for times of monitoring individual items):

1. Weight
2. Vital signs
3. Continuous heart rate monitoring will be recorded during IV Ghrelin and IV alcohol co-administration.
4. BrAC, breath carbon monoxide (BrCO); Blood Alcohol Content (BAC) when participants are in the fMRI scanner.
5. Drug use: Urine Drug Test (UDT)
6. Blood Test Panel I: blood glucose, cholesterol, triglycerides, GH, insulin, IGF-1, cortisol, ACTH, PRL, FSH, LH, testosterone total and free, T3-free, T4-free, TSH.
Blood Test Panel II: GH, insulin, cortisol, PRL (and other feeding and stress related hormones).
7. Urinalysis
8. Pregnancy: urine pregnancy testing
9. Mood and anxiety level and suicidality (Comprehensive Psychopathology Rating Scale – CPRS), Columbia Suicide Severity Rating Scale (C-SSRS).
10. Alcohol consumption- TLFB and alcohol craving (A-VAS and AUQ)
11. NMR Safety Questionnaire- questionnaire developed by NMR Center to verify absence of any exclusions to MRI scanning (to be completed at screening and visits 4 and 5).

Toxicity tables/criteria to be used

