NCI Common Terminology Criteria for Adverse Events v. 3.0 will be used for grading and reporting adverse events.¹⁶⁷

Criteria for individual subject withdrawal

- A Serious Adverse Event (SAE) that is judged by the Investigators as being related to the study drug;
- Pregnancy;
- At the discretion of the Principal Investigator (PI) based on adverse event (AE) severity;
- Non-compliance with protocol procedures or investigator request(s);
- Patient request.

Enrolled subjects who show up with positive UDT or BrAC $\geq 0.08\%$ at one of the four experimental sessions (excluding the night before visits 2-5) will not perform the session. In this case, the experimental session may be re-scheduled at the PI discretion. Additionally, a session may be rescheduled for other medical reasons for which the PI and/or MAI think it is in the best interest of the participant to re-schedule the session. However, if the subject will repeatedly show up with positive UDT or BrAC $\geq 0.08\%$ at repeated visits, the PI may withdraw him/her from the study.

9. Outcome measures

a. Primary outcome measures

The primary measure of this study will be the breakpoint, which is the schedule (number of button presses) at which the individual stops to work for more alcohol during the PR sessions.

b. Secondary outcome measures

Alcohol exposure will be measured via BrAC exposure measures, i.e. highest BrAC, average BrAC and the area under the BrAC-time curve and by BAC when subjects are in the fMRI scanner. Alcohol craving will be measured using the Alcohol Visual Analogue Scale (A-VAS) and the Alcohol Urge Questionnaire (AUQ). Sensitivity to alcohol will be measured using the Drug Effects Questionnaire (DEQ), Biphasic Alcohol Effects Scale (BAES), and the Profile of Mood States (POMS), repeatedly during the PR session and the CASE Experience Questionnaire (CEQ)

at the end of all sessions. fMRI BOLD signal in brain areas associated with incentive salience and areas associated with reward circuitry (including the ventral striatum) will be measured during the “fMRI/alcohol clamp” session.

10. Statistical Analysis

1. Analysis of data/ study outcomes

Analysis of data/study outcomes

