Outcome data will be examined for homogeneity of variance, and if necessary transformed to meet this criterion. Most of the analyses will consist of repeated measures ANCOVAs to accommodate dependent measures assessed at multiple time points. When the dependent measure is just assessed once then a regular ANCOVA will be used. We will examine medication main effects across several different dependent measures.

Criteria for significance

A probability level of 0.05 or lower will be considered significant.

2. Power analysis

Power analysis

A generic calculation of power for a two-means comparison to detect an effect size of Cohen's $f \geq 0.4$ (large effect size) with a sample size of 50 yields a power estimate ≥ 0.80 at alpha=0.05. The relative effect size chosen (“large” effect size) for the power calculation is based on the observation that laboratory studies typically yield larger effect sizes than clinical trials, including, for example, our recent (unpublished; PI: [name]) human lab studies using the

IV Alcohol PR procedure, described above and representing the study our primary aim (number of button presses) is based upon.

Furthermore, the sample proposed here provides sufficient power (power estimate ≥ 0.80 at alpha=0.05) to detect ghrelin's effects on fMRI BOLD activation in the VS, consistent with the unpublished data (PI: [name]; data already mentioned above) with varenicline (n = 8) vs. placebo (n = 7) indicating significantly higher BOLD activation in the varenicline group.

Accrual number request, taking into account screening/ dropouts

In the Brown University study with IV ghrelin, inclusionary/exclusionary criteria were similar and about 50% of the subjects screened were eligible and randomized. Consistent with other human laboratory studies with a similar study length, we also expect that a number up to 20% will not complete the study. Therefore, we anticipate a number-needed-to-screen of 124 subjects, with 62 being randomized and 50 completers.

11. Human Subjects Protection

a. Subject selection

Adults who fulfill the qualification criteria will be included, regardless of race, ethnicity, sex, or religious affiliation.

b. Justification for inclusion of children

Children will not be included because the study proposed involves the administration of alcohol. It is illegal to give alcohol to individuals below 21 years of age.

c. Justification for inclusion or exclusion of other vulnerable subjects

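### Blood pressure and heart rate, the plan's own named haemodynamic risk, have no planned ghrelin-versus-placebo comparison; the safety aim is assessed through adverse events only

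*Combined protocol and SAP*

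**What the plan says.** Section 7, under IV Ghrelin administration (item 3), states: "IV Ghrelin has been associated with decreased arterial pressure and secondary increased heart rate can also occur". Under IV Ghrelin and IV alcohol co-administration, the same section lists lower pressure among the possible additive effects and handles it by exclusion and monitoring: "Decreased arterial pressure; thus, we will exclude individuals with history of hypotension clinically significant", followed by the commitment that "blood pressure and continuous heart rate will be monitored during the lab and fMRI sessions".

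Section 8 puts vital signs in the safety battery, of which it says "They will undergo standard assessment battery (described below) at each study visit". It adds: "Continuous heart rate monitoring will be recorded during IV Ghrelin and IV alcohol co-administration". Measurement times are left to a study flow sheet that is not in the available text. Section 4 (Overnight stays) adds vital signs roughly every 30 minutes after each session until breath alcohol returns to zero.

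The safety objective, in Section 2b, reads: "Adverse events will also be assessed in order to assess the safety of the IV co-administration of ghrelin and alcohol". Section 9 names breakpoint as the primary outcome. Its secondary list covers alcohol exposure, craving, sensitivity questionnaires and BOLD signal, and contains no blood pressure, heart rate or other vital sign. Section 10 describes ANCOVAs in general terms and says: "We will examine medication main effects across several different dependent measures". It does not name those measures and contains no safety analysis.

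**The concern.** The plan identifies a specific physiological harm, observes it on a continuous scale under both drugs in the same person, and then does not ask the data whether ghrelin moved it. The safety conclusion would rest on whether somebody recorded an event.

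The protocol's own literature summary shows how that can lose information. The Introduction reports that IV ghrelin significantly lowered blood pressure in a study of patients with chronic heart failure (reference 70). The adverse-event column of Table 2 for that study shows only warmth and sleepiness. Section 7 then cites Tables 1 and 2 in support of a very safe profile.

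The safety conclusion also matters to the design. The Introduction (PR IV Alcohol Procedure) says the PR sessions will establish the safety of co-administration before the same volunteers go on to the fMRI/clamp sessions. A report that co-administration was well tolerated could be issued while a consistent shift in pressure or heart rate sat unanalysed in the trial's own records.

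**Working it through.** **1. The plan's own figure.** The only worked figure in Section 10 is power of at least 0.80 for Cohen's f of 0.4 with 50 participants at alpha 0.05. For two means, f = 0.4 corresponds to d = 0.8. Two groups of 25 give 0.807 by the normal approximation and 0.791 by the exact t-test. A paired t-test with 50 pairs and a standardised difference of 0.4 gives 0.792. The figure reproduces to within rounding, and the present point does not depend on it.

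**2. Where the two measures appear.**

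| Part of the plan | Blood pressure | Heart rate | Adverse events |
|---|---|---|---|
| Section 7, named risk | yes | yes (secondary rise) | – |
| Sections 7 and 8, observed in sessions | monitored; vital signs | monitored and recorded | yes |
| Section 2b, safety objective | no | no | yes |
| Section 9, outcomes | no | no | no |
| Section 10, named in an analysis | no | no | no |
| Section 16, summarised at continuing review | no | no | yes |

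The last column shows a related gap: adverse events are the stated safety objective, yet they too are missing from Section 9 and have no analysis method in Section 10.

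**3. What event counts alone can say.** Suppose no hypotension event is recorded in the 50 planned completers. The exact one-sided 95% upper limit for the event risk is 1 − 0.05^(1/50) = 5.8%. That bounds how often an event occurs. It gives no information on the size of an average shift.

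**4. What the paired data could say.** Inputs: n = 50 pairs (Section 10) and t(0.975, 49 df) = 2.01. The standard deviation (SD) of the within-person difference is not in the documents, so 8 to 15 mmHg is assumed. Half-width of the 95% interval = 2.01 × SD / √50:

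| Assumed SD (mmHg) | Half-width (mmHg) |
|---|---|
| 8 | 2.3 |
| 10 | 2.8 |
| 12 | 3.4 |
| 15 | 4.3 |

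A modest average fall could therefore be estimated usefully without adding participants.

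**5. What the contrast would mean.** In the PR sessions alcohol is self-administered, up to a breath level of 0.12, and Section 11d states the hypothesis that ghrelin will raise self-administration. A ghrelin-minus-placebo difference there combines any direct effect of ghrelin with the effect of a different alcohol intake. For the clamp sessions the Precis calls the alcohol dose fixed, but the Precis and Section 4 also say that points earned in the MID task determine how much alcohol is given. Those statements need to be reconciled before the clamp contrast can be read as one at equal alcohol exposure. All four sessions include alcohol, so neither pair isolates an interaction between the two drugs.

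**The case against.** A reader might infer that a ghrelin-induced fall in pressure would go unreported or unnoticed. The documents do not support that. The independent safety monitor reviews individual and cumulative data, including relevant clinical data, receives weekly safety reports and may break the blind. Infusions are stopped, and the IRB notified, if significant symptoms require it. The open wording of Section 10 does not forbid an analysis of blood pressure. What stands is narrower: none of these provisions commits anyone to a comparison by drug, and individual review is poorly suited to detecting a small average shift.

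A reader might also speak of falls below the adverse-event threshold. The text gives no numeric limit for blood pressure or heart rate, only a reference to CTCAE v3.0, so no such threshold can be stated. Nor does adverse-event reporting always miss the effect: Tables 1 and 2 list decreased pressure as an adverse event for three other studies (references 32, 79 and 87).

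The strongest practical objection concerns capture. Heart rate is said to be recorded; blood pressure is said only to be monitored, at times given in an unseen flow sheet. The lowest of an unknown number of readings depends on how many were taken, so a lowest-value endpoint cannot be justified from the text. This stands, and it is why the fix uses readings at scheduled times common to both sessions.

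It would also be tempting to count sessions with systolic pressure below 100 mmHg. That figure is an enrolment limit. A person enrolled at exactly 100 would be counted after a change of 1 mmHg, and nothing in the documents supports it as an on-treatment cut-off.

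Finally, this is a mechanistic laboratory study with breakpoint as its primary outcome, and two vital signs are not central to it. That limits the weight of the point. It does not remove it, because safety of co-administration is a stated aim.

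**Conclusion.** The point holds as a gap in planned analysis. The named haemodynamic risk is observed under both drugs in every participant who completes a session pair, and no ghrelin-versus-placebo comparison of it is planned. A consistent sub-clinical shift would appear in no planned analysis. It does not follow that participants are unmonitored or that a clinically evident fall would be missed.

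The precision forgone is a 95% interval of about ±2.3 to ±4.3 mmHg. This rests on 50 complete pairs, the assumed SD range, and blood pressure being recorded at matching times in both sessions of a pair. Fewer complete pairs would widen it. It is a minor improvement: it strengthens the answer to a secondary safety aim and does not touch the primary result.

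**What to change.** In Section 9b, list blood pressure and heart rate as safety outcomes. In Section 10, add within-person ghrelin-minus-placebo estimates with 95% confidence intervals:

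- Use change from that session's pre-bolus value.
- For blood pressure, use readings at the scheduled times common to both sessions of a pair. For heart rate, use the continuous record. Include the post-session vital signs.
- Report the PR pair and the fMRI/clamp pair separately.
- Present these as safety estimates, not hypothesis tests.
- Show breath or blood alcohol by drug beside them, and state that the PR contrast is a total effect that includes any change in self-administered alcohol.
- Do not add a count below 100 mmHg.

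In the same edit, add adverse events to Section 9 and say how they will be tabulated by drug.

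The cost is a few lines of text and one extra table. No participants are added and no clinical procedure changes. That no new readings are needed should be confirmed against the flow sheet, in particular that a pre-bolus blood pressure is scheduled.

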Eligible participants will be randomized to 1 of 2 counterbalanced arms to receive first either ghrelin or placebo during the first PR session. Participant then will receive the alternate condition during the second PR session. Similarly, participants will receive ghrelin first and then placebo (or vice versa) during the third and fourth sessions, namely the two “fMRI/alcohol clamp” sessions. Eligible participants will be randomized to receive either ghrelin or placebo during the study according to gender, based on a stratified block design. The Pharmaceutical Development Service (PDS) of the NIH CRC will develop the randomization schedule and maintain the blind; they will also be responsible for determining subject allocation. The allocation code will be kept in a safe location at the pharmacy, with access only for the responsible pharmacist. In emergency medical situations, which may require premature breaking of the code, the PI will be able to obtain access to the code table through the pharmacist on duty; this will then be documented, and reported to the IRB.

d. Study Procedures

Visits and procedures

IV Ghrelin infusion: dose justification

Overview.

After a 10 minute bolus of IV ghrelin or matched placebo (saline solution), IV ghrelin or placebo infusion will last 120 min during visits #2 and #3 (120 minutes is the duration of the alcohol PR session) and 65 min during visits #4 and #5 (the total duration of the fMRI/alcohol clamp is 95 min with 35min for the alcohol clamp – details below and in appendix flow sheets). The Pharmaceutical Development Service (PDS) of the NIH CRC will prepare the ghrelin bags ready for IV infusion. Vials of ghrelin and saline will be indistinguishable visually.

Dose.

A bolus of IV ghrelin followed by an infusion of IV ghrelin will be employed, as detailed next.

- An IV administration of 3 mcg/kg bolus of ghrelin. The injection of the bolus will start 10 minutes before the start of the other lab procedures (PR for Visits #2 and #3; “fMRI/alcohol clamp” for Visits #4 and #5) and will last 10 minutes;
- An infusion of 5 pmol/Kg/min (that is 16.9 ng/kg/min) of ghrelin for 120 minutes (Visits #2 and #3) or 65 minutes (Visits #4 and #5). In fact, the infusion will last for the duration of the PR (120 minutes at Visits #2 and #3) and for a portion of the 95 min “fMRI/alcohol clamp” (65 minutes at Visits #4 and #5).

Dose justification.

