The PR schedule self-administration will be conducted using the Computer-Assisted Self-infusion of Ethanol (CASE) system (currently being used in two NIH protocols 08-AA-0137 and 08-AA-0178). Just prior to the start of the PR schedule session, the subject will be reminded of the procedure for obtaining alcohol during the session. Following a 15-min priming interval (that will not be applied here, as our ‘priming’ is the IV bolus of ghrelin), the PR period lasting 120 minutes begins. Each standardized exposure will follow a slopelet pattern (linear increase of 7.5 mg% over 2.5 min followed by a linear decrease of 0.5 mg%/min until the next exposure). The PR schedule will escalate geometrically from using a progressive ratio that will be empirically established. An initial PR schedule will be established based on simulations using the model published by Richardson and Roberts.¹⁴⁷ For practical considerations, we will select a schedule that requires 2 button presses for the first exposure and escalates exponentially to requiring ~15,000 button presses for the 20th exposure. This initial schedule will be tested in the first 6 subjects, and the range of break-points obtained will be evaluated. If there is insufficient variability in the break-points across the first 6 subjects, the schedule may be adjusted before proceeding with the enrollment of other subjects. Within 0.5 seconds of pushing the drink button, the CASE system software will begin infusing the alcohol necessary to produce the desired increase in BrAC exposure from the BrAC level at the time the button was pushed. Also, if the CASE system predicts that an additional drink selected by the participant would result in a peak BrAC 0.12 (which is the upper limit for BrACs achieved in this study), then the push button will be inactivated, with the subject’s knowledge, until the time when the predicted peak BrAC is below the upper limit.

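### The 120-minute limit turns the primary breakpoint into a lower bound for anyone still pressing, and the planned ANCOVA cannot treat it as one

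*Combined protocol and SAP*

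**What the plan says.** The primary outcome in section 9a is the breakpoint, "which is the schedule (number of button presses) at which the individual stops to work for more alcohol during the PR sessions". The précis and section 2a define it in the same way, by the participant's own decision to stop.

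The procedure adds a fixed limit. In section 4d, under the PR self-administration heading, "the PR period lasting 120 minutes begins". The ghrelin infusion overview in the same section confirms that "120 minutes is the duration of the alcohol PR session". The chosen schedule "requires 2 button presses for the first exposure and escalates exponentially to requiring ~15,000 button presses for the 20th exposure". It is provisional: the range of breakpoints in the first six subjects will be evaluated, and "If there is insufficient variability in the break-points across the first 6 subjects, the schedule may be adjusted".

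A second limit concerns breath alcohol. If another exposure is predicted to reach 0.12, "then the push button will be inactivated" until the predicted peak is back under the limit.

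Section 10.1 plans repeated-measures or ordinary ANCOVA, with a transformation if variances are unequal. Nothing in the document says what breakpoint is recorded when the clock ends responding.

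**The concern.** The definition needs a voluntary stop, but the procedure can end a session without one. A participant working on an unfinished requirement at minute 120 has shown motivation at least as high as the last completed step. How much higher is not observed. An ANCOVA takes whatever number is entered as the outcome itself, and no variance-stabilising transformation recovers information above a ceiling.

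The hypothesis is that ghrelin raises self-administration, so ghrelin sessions would meet the ceiling more often than placebo sessions. That compresses the contrast the trial is meant to estimate. For persistent participants, the highest attainable value also depends on how fast they press. A ghrelin effect on pressing speed would then be mixed with motivation; section 7 lists sedation among the possible additive effects of ghrelin and alcohol.

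**Working it through.** **The plan's power figure.** Section 10.2 claims power of at least 0.80 for Cohen's f = 0.4, N = 50, alpha 0.05. With f = 0.4 read as d = 0.8 and 25 per group, two-sided, the normal approximation gives 0.807 and the t distribution 0.791. A paired test with n = 50 and standardised difference dz = 0.4, closer to the actual design, gives 0.792. The claim reproduces, with no margin.

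**The schedule (section 4d).** A geometric rise from 2 to 15,000 over 20 steps has ratio (15,000/2)^(1/19) = 1.599. The total is 2 × (1.599^20 − 1)/(1.599 − 1) = 40,023 presses, using the unrounded ratio. Over 120 × 60 = 7,200 s this is 40,023/7,200 = 5.56 presses per second without pause. Cumulative totals are 3,821 (step 15), 6,114 (16), 9,780 (17), 15,644 (18) and 25,023 (19).

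**Where the clock stops someone who never quits.** Pressing rates are assumed, since the documents give none. A step counts if its cumulative presses divided by the rate fit within 7,200 s. The lower step assumes that pressing waits for each 2.5-minute rise; the higher assumes continuous pressing.

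| Presses/s | Last step completed | Requirement at that step |
|---|---|---|
| 1 | 15–16 | 1,433–2,292 |
| 2 | 16–17 | 2,292–3,666 |
| 3 | 17–18 | 3,666–5,864 |
| 5 | 18–19 | 5,864–9,379 |

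Example at 1/s: 6,114 s = 101.9 min for step 16 if pressing is continuous. Adding 15 rises × 2.5 min = 37.5 min gives 139.4 min, over the limit, so step 15 is the last.

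**Breath-alcohol limit.** The exposure profile is a "linear increase of 7.5 mg% over 2.5 min followed by a linear decrease of 0.5 mg%/min until the next exposure". Stepping through it with pressing allowed during the rise, the modelled level peaks at 118.7 mg% at 5 presses/s. The button is inactive for 0.2 min at 5.56/s and 3.2 min at 6/s. At slower rates the clock is the only limit that acts.

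**Effect on the test.** Simulation of paired normal breakpoints: n = 50, dz = 0.4, between-session correlation 0.8 (assumed), common ceiling, 20,000 trials per setting.

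| Placebo sessions at ceiling (assumed) | Share of true difference estimated | Power |
|---|---|---|
| 0% | 100% | 0.79 |
| 5%* | 93% | 0.78 |
| 10% | 88% | 0.76 |
| 20% | 76% | 0.70 |
| 30% | 66% | 0.65 |

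*Run at dz = 0.404, where uncensored power is 0.80.

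With correlation 0.6, the 10%, 20% and 30% rows become 86%, 74% and 64%, with power 0.75, 0.71 and 0.66. With no true effect, rejection stays near 0.05 throughout.

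A common ceiling is a simplification, because the real one varies with pressing speed. With person-specific ceilings correlated with motivation (correlation 0.8 assumed), the paired analysis keeps about 94–95% of the effect at 5% cut off, and about 76% and 66% at 20% and 30%. At those last two shares, a random-intercept censored model recovers about 96–104% of the effect, gains about 3–5 power points and holds type I error near 0.04.

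**The case against.** The strongest reply is that nothing shows the clock binds. The escalation makes persistence costly: step 16 needs 6,114 cumulative presses for one more 7.5 mg% rise, while music, videos or the internet are on offer. If only 1% or 2% of placebo sessions were cut off, 99% or 97% of the effect would remain. This stands, and it is why the size is left open.

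Four stronger readings are tempting, and the documents do not support them.

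- **The plan instructs that clock-ended values be treated as exact.** It is silent. That treatment follows only because ANCOVA is the sole method named. Sections 2b and 10.2 also gloss the outcome as a number of button presses. Read as total presses in a fixed period, it would be fully observed, though still bounded by speed.
- **The breath-alcohol limit also ends sessions.** The inactivation is temporary, so it is a pause.
- **The six-subject review is blind to a ceiling.** It evaluates the range of breakpoints, and bunching at a common ceiling would show there. Low variability is, however, the only stated trigger for adjustment, and ceilings that differ between people can leave ample variability.
- **The result could be falsely positive.** With equal pressing speed in both conditions, the bias is toward zero.

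A fair objection to any censoring remedy is that no inactivity or quit rule exists, so voluntary stopping cannot be coded until it is defined. Slow pressing may also itself reflect low motivation, so censoring may not be independent of the outcome. Both points shape the fix.

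**Conclusion.** The concern holds as a gap between the definition of the sole primary endpoint and the way it is observed. On the documents' own figures, the provisional schedule cannot be finished below about 5.6 presses per second, so a participant who does not quit gives a lower bound. The named analysis cannot use it as such.

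The consequence is conditional. If clock-ended sessions occur, the effect is attenuated and power falls from a starting point of about 0.79–0.81. The attenuation figures rest on assumed shares of cut-off sessions, an assumed between-session correlation and normal latent breakpoints. They show the scale and do not forecast this trial. The schedule may also change after six subjects, which would move the step figures. Left unspecified, the scoring rule could be chosen after the data are seen.

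**What to change.** 1. Score the breakpoint as the last completed step, and analyse it on the step or log scale.
2. Flag a session as clock-ended from time-stamped button presses, by a rule fixed before unblinding: for example, still responding on an uncompleted ratio within a prespecified window before 120 minutes. Treat breath-alcohol inactivation as a pause and not as a session end. Report the number of clock-ended sessions by condition.
3. Prespecify a within-person censored model alongside the planned ANCOVA: a random-intercept Tobit model, right-censored at the last completed step for clock-ended sessions. Showing both lets a reader judge how far the result depends on the censoring assumption.
4. At the existing six-subject schedule review, look at the pooled, blinded share of clock-ended sessions as well as variability and range.

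The cost is choosing and justifying the stopping window, keeping the press times (assumed to be available, since CASE is computer-run), and a small amount of extra analysis. If clock-ended sessions prove rare, the two analyses will agree. Session length and the breath-alcohol limit are unaffected.
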